7.1 SCREENING SESSION (VISIT 1)

The following study procedures will be performed:

1. Written informed consent from study participant
2. Demographic Information
3. Physical Activity Scale for the Elderly Questionnaire (PASE)
4. The Mini Mental State Examination (MMSE)
5. The Montreal Cognitive Assessment (MoCA), Logical Memory 1 & 2, Consortium to Establish a Registry for Alzheimer's Disease (CERAD) Word List Recall
6. Geriatric Depression Scale (GDS-30)
7. Generalized Anxiety Disorder 7 (GAD-7)
8. Clinical Dementia Rating Scale (CDR)
9. Alzheimer's Disease Cooperative Study Activities of Daily Living (ADCS-ADL) and Lawton Brody Instrumental Activities Of Daily Living (IADL) Scale
10. Physical Activity Readiness Questionnaire Plus (PAR-Q+)
11. Physical Activity Tracker allocated to study participant

During the screening session, global cognitive function will be assessed using the MMSE and the MoCA[40,41] and Physical Activity Readiness Questionnaire Plus (PAR-Q+) will be also done. Physical activity trackers (ActiGraph) will be provided to each participant during the screening session. The physical activity tracker will be worn by participants until first baseline assessment visit, which is scheduled up to four weeks after screening. This strategy will assure an accurate record of physical activity for each participant prior to participating in the training protocol and will be correlated with the response on the PASE questionnaires.

Height, weight, seated and standing blood pressure, resting heart rate will be measured at screening session. Participants will undergo a clinical assessment with baseline to confirm current health status and eligibility for study using the PARQ+.

The participant will be asked to bring an informant with them to complete the CDR. If the participant does not have an informant to attend the visit with them, the informant portion of the assessment can be completed with the informant by phone the day of the visit. This will be arranged and completed by a trained Research Assistant or Coordinator.

7.2 BASELINE EVALUATION (VISIT 2)

Participants will undergo rigorous baseline evaluations, which will take place up to four weeks after the screening session. Baseline assessments will include neuroimaging, neuropsychological, and gait measures. These will be repeated at the 6-month and 12-month follow-up.

1. Log return of the Physical Activity Device
2. Blood Draw
3. Clinical Medical Questionnaire
4. Quality of Life Questionnaire (SF-36)
5. ADAS-Cog Plus Tests (ADAS-Cog 13 Tests, plus the Digit Span Forward and Backward WAIS-III, TMT A and B, Digit Symbol Test, Boston Naming Test)
6. D-KEFS Colour Word Interference Test
7. Short Physical Performance Battery (SPPB)
8. Six Minute Walk Test (6MWT)
9. Dual task control assessment while seated (mental task)
10. Gait assessment using Gait Mat and Accelerometers (when available)
11. Schedule Neuroimaging

7.2.1 TREATMENT ALLOCATION

Randomization Once informed consent has been obtained and the baseline assessment has been completed, participants will be allocated to each of the 5 arms. The randomization sequence of the participants will be generated in each site with a minimum of 4 participants recruited using a central, web-based randomization service. The Research Pharmacy will assign the ‘vitamin D/placebo kits’ in compliance with randomization lists generated by a computer program and allocation to groups will be done with sequentially numbered opaque sealed envelopes. A block randomization by 5 will be applied to ensure an appropriate balance of the characteristics of participants between each arm. Permuted

blocks of varying size will be employed to ensure balance over time. After baseline assessment, research personnel not involved in measurement or intervention will access the web-based randomization service to determine the group allocation.

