5. STUDY POPULATION

5.1 PARTICIPANTS, RECRUITMENT, STRATIFICATION, AND BLINDING

We will target older adults aged 60 and over with MCI. Interventions will be done across five sites: London (lead and sponsor site, target recruitment: 70 participants), Waterloo-University of Waterloo (target recruitment: 25), Waterloo-Wilfrid Laurier University (target recruitment: 20), Montreal (target recruitment: 30) and Vancouver (target recruitment: 55). Each intervention site may have more than one recruitment center. For those who are interested in participating, a consent and screening session will be arranged as described in our participant flowchart, Figure 3.

Once informed consent is obtained, we will perform the screening tests. Those who remain eligible after the screening session including the Physical Activity Readiness Questionnaire Plus (PARQ+) and who provide written recommendation from their physician or site physician indicating their appropriateness to participate in an aerobic-based exercise training program will proceed to baseline assessments. Participants will be informed that they will be randomly assigned to one of five arms by the research coordinator and will be blinded to the investigators' hypothesis as to which is the preferred intervention arm.

All groups will have an equal volume and frequency of contact with trainers over the 12 months of the study. All primary and secondary outcomes will be obtained and analyzed by blinded assessors on different days to the training programs.

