5.2 INCLUSION AND EXCLUSION CRITERIA

Inclusion criteria:

Participants must meet each of the following criteria for enrolment into the study:

1. At least 60 years of age.
2. Self-reported levels of proficiency in English or French (at Montreal site only) for speaking and understanding spoken language.
3. Able to comply with scheduled visits, treatment plan, and other trial procedures.
4. Able to ambulate at least 10 m independently.
5. Having MCI defined following Albert et al.[28] criteria as:
a-Objective cognitive impairment in one of the following four cognitive domains: memory, executive function, attention, and language operationalized using one or more of the following: MoCA Test (Montreal Cognitive Assessment) with scores ranging from 13-24/30, Logical Memory below ADNI cutoffs, CERAD word list recall < 6.

b-Preserved activities of daily living operationalized as a Score >14/23 on the Lawton-Brody IADL[29] scale and confirmed by clinician's interviews.

c-Absence of dementia using criteria from the Diagnostic and Statistical Manual of Mental Disorders, Fifth Edition [30] and/or Global CDR = 0.5.

6. Having normal or corrected to normal vision in at least one eye so that they can identify symbols and stimuli presented on a computer screen in front of them.
7. Must be in sufficient health to participate in the study's aerobic-based exercise training program. This will be determined using the PARQ+ screening tool and with an evaluation by a certified exercise physiologist and/or a physician, when appropriate indicating clearance to participate in an aerobic-based exercise training program.

Exclusion criteria:

Participants who exhibit any of the following conditions are to be excluded from the study:

1. Serious underlying disease which, in the opinion of the investigator, may preclude engagement in interventions or may interfere with the participant's ability to participate fully in the study.
2. Participant with uncontrolled major depression, schizophrenia, severe anxiety and drug abuse.
3. Current parkinsonism or any neurological disorder with residual motor deficits (e.g. stroke with motor deficit), active musculoskeletal disorders (e.g. severe osteoarthritis of lower limbs) or history of knee/hip replacement affecting gait performance at clinical evaluation
4. Intention to enroll in other clinical trials during the same time period.

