7.6.6 MOBILITY OUTCOMES

Gait velocity and variability (single and dual-tasking)

Gait velocity will be assessed as the time taken to walk the middle 6 meters of 8 meters using the Portable Walkway System (ProtoKinetic® and/or GAITRite® Systems, Inc.) These devices automate the acquisition, analysis, and reporting of the objective parameters of gait as the subject walks down the walkway with embedded sensors. As a result, these gait mats allow detecting subtle changes in gait, including gait variability since it has been proven to have a fine discrimination when compared with other quantitative methods.[50] The gait mat is located in a well-lit room with start and end points marked on the floor one meter from either end of the mat to avoid recording acceleration and deceleration phases.

Instrumentation:

Gait performance will be assessed using electronic walkway systems (GAITRite® or PkMas®), which automatically determines spatiotemporal gait parameters from imbedded sensors activated by foot pressure. A computer processes the footsteps, providing data for both spatial and temporal parameters. In addition, among sites without electronic walkway systems, quantitative gait parameters will be assessed using wearable inertial sensors (Gulf Coast Inc.; Shimmer Inc.) worn bilaterally on the ankles and at the hip. Acceleration data will be used to calculate foot-contact and foot-off times determine step and stride timing data. Overall gait velocity is determined by timing the standard walk distance.

For walking conditions all individuals will perform walks along a 6 meter path while wearing hip and ankle worn accelerometers. Individuals will perform three main tasks: 1) preferred walking speed, 2) dual task walking and 3) fast walking. In the case that a participant uses an assistive aid (cane, walker), the tester will determine the participant's capacity to walk safely without the use of the aid. With the

willingness of the participant, they will then perform one test walk without the use of the aid. If the participant is able to safely walk without the use of the assistive aid, all subsequent testing will be performed without its use. In all walks, participants will start 1 meter before the beginning of the 6 meter platform and continue to travel 1 meter past the end of the platform. This procedure is in place to ensure steady-state walking and to minimize any effects of acceleration and de-acceleration during the course of the walk.

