153 AP/PA correction scan = 7 min) to calculate fractional anisotropy and diffusivity in white
154 matter tracts as well as derive tract-based statistics. Cerebrovascular integrity and
155 pathology will be assessed using the following contrasts: PD/T2 = 5 min; FLAIR = 7 min,
156 and T2* = 5 min). Functional magnetic resonance imaging at rest (rsfMRI plus field map
157 = 12 min) will also be acquired to measure change in data-driven functional networks.

158 **9.5 Change in Blood biomarkers measures**

159 Serum biomarkers of inflammation (C reactive protein, and interleukin 6), neuroplasticity
160 (brain-derived neurotropic factor), endothelial health (vascular endothelial growth factor
161 1), and vitamin D serum levels will be measured before and after intervention.

162 **9.6 Covariates**

163 Pre-specified covariates will be age, sex, years of education and number of
164 comorbidities.

165

166 **10. Statistical Analysis**

167 **10.1 Descriptive Analysis**

168 The baseline characteristics will be summarized using means and standard deviation, or
169 medians and interquartile range where appropriate, for continuous characteristics, and
170 frequencies and percentages for categorical variable.

171 **10.2 Primary Efficacy Analysis**

172 The primary analysis will be based on the intention-to-treat principle, including everyone
173 who were randomized. Comparisons between arms will be conducted according to pre-
174 specifications in the protocol. These comparisons align well with the recommended
175 analysis and reporting of factorial trials⁵, which used “inside the table” and “at the
176 margin” analyses for different comparisons. The “inside the table” analysis will be used
177 to compare each intervention effect to control, while “at the margins” analysis will be
178 used to assess the effect of adding intervention.

179 The major interest would be the effect of the intervention on change in primary
180 outcomes at 6 Month compared to the control arm (arm 5). The primary outcome
181 measure of mean change in ADAS-Cog-13 and ADAS-Cog-Plus scores will be analyzed
182 using a linear mixed model with restricted likelihood estimation. The model will be fitted
183 with participant-specific random intercept and fixed effects of time, intervention arm, and
184 time x intervention arm interaction. The time variable will be used as a categorical
185 variable (0 = baseline; 1 = Month 6.) The intervention arm variable will be dummy

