186 coded, using the control group as a reference category. The interaction term will be

187 used to assess between-group differences (representing a mean difference in change in
188 cognitive scores over time between two groups). With dummy coding of the intervention
189 arm, the interaction term will allow to compare the mean change in each intervention
190 arm to the arm 5 (control). The within-group difference (representing a mean change in
191 cognitive scores over time within the group) will be measured with marginalized mean
192 from the linear mixed regression model. The model will be further adjusted for
193 participant characteristics including age, sex, education, and comorbidities.

194 An unstructured covariance matrix will be used for all models. The model assumption
195 will be assessed using the normal quantile plots of residuals for normality and the
196 residuals vs. fitted plot for variance homogeneity. If the assumptions are not fully met,
197 the data will be transformed (i.e., log). Missing data will not be imputed and will be
198 assumed to be missing at random, as the mixed model approach is well-known to
199 handle such data effectively.⁶ The baseline data from individuals who did not complete
200 Month 6 assessment will be included in the linear mixed model.

201 The mean difference between groups will be presented with their 95% CI and p-value,
202 while the mean change within group will be presented with their standard error. The
203 obtained marginalized mean and standard deviation will be used to calculate the effect
204 size (
$$\frac{\text{mean change in treatment } X - \text{mean change in treatment } Y}{\text{pooled standard deviation of change}}$$
). As outlined in our published
205 protocol, we will calculate the proportion of participants with improvement in primary
206 outcomes.

207 All tests will be two-sided, and p-value of less than 0.05 will be considered as
208 statistically significant. Adjustments for multiple comparisons will not be made as the
209 trial is intended to compare the intervention effect to the control rather than pairwise.⁷
210 Per-protocol analysis will be performed as well.

211 As per recommended analyses of fractional factorial design⁸, “at the margin” analyses
212 will be performed by collapsing arms according to the pre-specified comparison.
213 Collapsing intervention arms allow to increase the study power to detect the difference

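### The allocation sequence is blocked within each site, but no SAP mixed model for the primary outcomes contains site or site x time, so the primary tests are slightly conservative

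*Combined protocol and SAP*

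**What the plan says.** **Randomisation.** Protocol 7.2.1: "The randomization sequence of the participants will be generated in each site with a minimum of 4 participants recruited", through a central web service. It continues: "A block randomization by 5 will be applied", and the same paragraph also mentions permuted blocks of varying size. Protocol 5.1: "Interventions will be done across five sites", with targets of 70, 25, 20, 30 and 55. The heading of 5.1 includes stratification, but its text names no stratification factor.

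**Analysis.** The SAP 10.2 primary model is fitted "with participant-specific random intercept and fixed effects of time, intervention arm, and" the time by arm interaction. It is then adjusted for "participant characteristics including age, sex, education, and comorbidities". SAP 9.6 gives the same list: "Pre-specified covariates will be age, sex, years of education and number of" comorbidities. SAP 10.2.1 to 10.2.4 reuse this model with arms pooled or take a term from it, and 10.2.5 extends time to three visits. None adds site. The repeated-measures ANCOVA in protocol section 8 adjusts for baseline only. SAP section 4 lists the sites as places of recruitment and gives them no role in the analysis.

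**Site differences on record.** Language, in protocol 5.2: "Self-reported levels of proficiency in English or French (at Montreal site only"). Gait equipment, in 7.6.6: "among sites without electronic walkway systems, quantitative gait parameters will be assessed using wearable inertial sensors".

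**The concern.** Blocking within site makes the arms nearly equal within each site, so site differences cancel from the arm comparison. A model without site does not know this. It counts between-site variation in change as noise, and the reported standard error then exceeds the true one. Precision that the design has secured is not used.

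Change could plausibly differ by site. Training is given in local groups of up to eight by local staff (protocol 6.1), and the amendment record allows virtual or in-person Month 12 assessment according to when each site reopened. At stake is a small amount of power for the contrasts of arms 1 to 4 with arm 5 and for the pooled comparisons.

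**Working it through.** **1. The plan's own figure.** SAP section 7 gives d about 0.5, 80% power and 15% attrition; SAP 10.2 gives two-sided 0.05.
- n per side = 2 x (1.96 + 0.842)^2 / 0.5^2 = 62.8, so 63.
- Two arms pooled per side: 63 / 2, so 32 per arm.
- 32 / 0.85 = 37.6, so 38 per arm, against 40 stated.
- The protocol's step 34 / 0.85 = 40 is exact.

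The target is therefore reproduced, to within two per arm, for the pooled cognitive-training and vitamin D comparisons. About 34 per arm are expected to be evaluable.

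**2. Effect of leaving site out.** Let rho be the share of the variance of change that lies between sites. The documents give no value, so 2%, 5% and 10% are assumed. With arms balanced within site:
- true SE = sqrt(1 - rho) x SE reported by the model without site
- type I error = 2 x [1 - Phi(1.96 / sqrt(1 - rho))]
- power without site = 1 - Phi[(1.96 x s - 0.5) / (s x sqrt(1 - rho))]
- power with site x time = Phi[0.5 / (s x sqrt(1 - rho)) - 1.96]

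Here s = sqrt(2/n). Example with n = 34 and rho = 0.10: s = 0.2425 and s x sqrt(0.90) = 0.2301. Power without site = 1 - Phi(-0.107) = 0.54. Power with site x time = Phi(0.213) = 0.58.

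| rho (assumed) | SE without / with site (simulated) | Type I error without site: formula; simulated | Power arm 1 v arm 5 (34 v 34): without; with | Power pooled pairs (68 v 68): without; with |
|---|---|---|---|---|
| 0 | not simulated | 0.050; 0.050 | 0.54; 0.54 | 0.83; 0.83 |
| 0.02 | 1.006 | 0.048; 0.047 | 0.54; 0.55 | 0.83; 0.84 |
| 0.05 | 1.018 | 0.044; 0.047 | 0.54; 0.56 | 0.84; 0.85 |
| 0.10 | 1.039 | 0.039; 0.043 | 0.54; 0.58 | 0.84; 0.87 |

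The SE ratios are for arms 1 to 4 v arm 5 (3,000 simulated trials per row, target site sizes, blocks of 5 within site, 85% retained). The simulated type I errors are for arm 1 v arm 5 (6,000 trials, blocks of 5 or 10, 15% dropout). Their Monte Carlo error is about sqrt(0.05 x 0.95 / 6000) = 0.003. With site in the model, simulated type I error was 0.046 to 0.052 across these rows.

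The formula gives a slightly larger effect than simulation because there are only five unequal sites. The squared site shares sum to (70^2 + 25^2 + 20^2 + 30^2 + 55^2) / 200^2 = 0.246, so on average only 0.754 x rho appears as between-site variance within one trial. At rho = 0.10 the SE ratio becomes sqrt((0.90 + 0.0754) / 0.90) = 1.041, close to the simulated 1.039. The formula's type I errors are therefore the larger estimate of the conservatism.

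**3. Which site term acts.** One simulated trial with complete data and a fixed site difference in level gave these REML fits:
- no site: time x arm estimate -1.332, SE 0.599
- site main effect: -1.332, SE 0.599
- site and site x time: -1.332, SE 0.603

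The main effect does nothing here because each participant's own baseline removes a constant site difference. SAP 10.2 keeps baseline-only participants, so with dropout the identity is no longer exact. In fits with 15% dropout the main effect moved the estimate by about 0.01. In another four simulated datasets it moved every time, in one from -0.801 to -0.888.

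**4. Price of the fix.** With 15% dropout and no site effect on change, site x time raised the SE by about 0.1% in one set of fits and by 0.3% to 1.0% in the four datasets above. With between-site variance of change of 0.05 to 0.10 against 0.98 within site, it lowered the SE by about 2% to 3%.

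**The case against.** **The effect is small, conservative and rests on assumed variances.** This stands. No conclusion of the trial is shown to change, and the case for a site term is efficiency and agreement with the design.

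**Site stratification is inferred.** The protocol speaks of a sequence generated in each site with a minimum of four participants, which might describe batching for group training. Blocked sequences generated site by site remain the plainer reading, but it should be stated as a reading.

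**Stronger readings.** A reader might infer any of the following, and the documents do not support them:
- *That language confounds the primary result.* A fixed French/English difference in score level largely cancels in change, and nothing in the documents says language alters change.
- *That unequal gait equipment undermines the primary analysis.* It bears on gait only. SAP section 9 keeps secondary outcomes out of the primary manuscript, and 10.3 leaves their models out of this SAP.
- *That a site term would repair unequal attrition across sites.* The documents report no attrition by site.
- *That a site main effect can never alter the contrast.* This is exact only with complete data.

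**Conclusion.** The mismatch is real: allocation is blocked within site, and no primary-outcome model contains site. Validity is intact. A reader might infer biased treatment effects or too many false positives, but arms balanced within site produce neither, and the planned tests err on the cautious side. The loss is a standard error 0.6% to 3.9% too large and up to about 4 points of power, for site shares of 2% to 10% of the variance of change. If site does not affect change, nothing is lost. These sizes assume site-stratified blocks, enrolment at the target site sizes and 15% attrition unrelated to site. The change is worth making because it costs little and because power for arm 1 v arm 5 is only 0.54 at d = 0.5 with 34 per arm.

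**What to change.** In SAP 9.6 and 10.2 to 10.2.5, add site (five levels, as randomised) and site x time as fixed effects to every linear mixed model for ADAS-Cog-13 and ADAS-Cog-Plus, including the three-visit model. Do not add site as a main effect only. Keep all five sites separate: merging small sites according to numbers seen at a visit would make the model data-dependent and would drop randomisation strata. State in protocol 7.2.1 or the SAP whether allocation is stratified by site. If outcomes have already been examined by arm, report the site-adjusted model as a declared sensitivity analysis.

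The cost is SAP wording and four parameters per visit, out of about 170 completers (200 x 0.85). Site should already be known for every participant. If site does not affect change, the standard error rises negligibly (0.1% to 1.0% in the fits above). Differences in gait equipment should be handled in the later plan for secondary outcomes.
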